2. The trial will be conducted in accordance with International Council on Harmonisation Good Clinical Practice (ICH GCP), applicable United States (US) Code of Federal Regulations (CFR), and the [specify NIH Institute or Center (IC) [Terms and Conditions of Award. The Principal Investigator will assure that no deviation from, or changes to the protocol will take place without prior agreement from the funding agency and documented approval from the Institutional Review Board (IRB), and the Investigational New Drug (IND) or Investigational Device Exemption (IDE) sponsor, if applicable, except where necessary to eliminate an immediate hazard(s) to the trial participants. All personnel involved in the conduct of this study have completed Human Subjects Protection and ICH GCP Training.

For either option above, the following paragraph would be included:

The protocol, informed consent form(s), recruitment materials, and all participant materials will be submitted to the IRB for review and approval. Approval of both the protocol and the consent form(s) must be obtained before any participant is consented. Any amendment to the protocol will require review and approval by the IRB before the changes are implemented to the study. All changes to the consent form(s) will be IRB approved; a determination will be made regarding whether a new consent needs to be obtained from participants who provided consent, using a previously approved consent form.

1 PROTOCOL SUMMARY

1.1 SYNOPSIS

Title:	The Effects of Incorporated Exoskeletal-Assisted Walking in SCI Acute Inpatient Rehabilitation
Study Description:	A randomized controlled trial
Objectives:	
Primary Objective: Primary Objectives: To determine the effects of acute inpatient rehabilitation (AIR) with exoskeletal-assisted walking (EAW) compared with AIR without EAW (same total therapy time) on the changes from admission to discharge in the International Standards for Neurological Classification of Spinal Cord Injury (ISNCSCI) upper and lower extremity motor scores, Functional Independence Measure (FIM) scores, and Spinal Cord Independence Measure (SCIM) scores as classified by clinicians. Primary hypothesis: At discharge, compared to the baseline data (collected at admission), the AIR with EAW group will have significantly greater changes in ISNCSCI, FIM, and SCIM scores compared to the AIR without EAW group.
 
Secondary Objectives: To determine the effects of AIR with EAW compared to AIR without EAW on reducing pain using the International Spinal Cord Injury Basic Pain Data Set 2.0 (ISCIBPDS 2.0) measures where type of pain is classified with the Spinal Cord Injury Pain Instrument (SCIPI). Secondary hypothesis: At discharge, compared with baseline, the AIR with EAW group will report significantly more reduction in the average intensity of the participant's worst pain over the preceding 7 days than the AIR without EAW group.
 
Tertiary Objectives: To determine the effects of AIR with EAW compared with AIR without EAW on reducing a specific systemic inflammatory mediator (C reactive protein, CRP). Tertiary hypothesis: At discharge, as compared with baseline, the AIR with EAW group will have greater reductions in measured values for CRP than the AIR without EAW group.

Endpoints:	
Primary Endpoint: The changes from admission to discharge in the International Standards for Neurological Classification of Spinal Cord Injury (ISNCSCI)

upper and lower extremity motor scores, Functional Independence Measure (FIM) scores, and Spinal Cord Independence Measure (SCIM) scores

Secondary Endpoints: Pain evaluation using the International Spinal Cord Injury Basic Pain Data Set 2.0 (ISCIBPDS 2.0) measures where the type of pain is classified with the Spinal Cord Injury Pain Instrument (SCIPI).

Tertiary Endpoints: systemic inflammatory mediator (C reactive protein, CRP)

Study Population: Individuals with SCI who stay in the SCI acute inpatient rehabilitation

Phase: NA

Description of Sites/Facilities Enrolling Participants: Icahn School of Medicine at Mount Sinai

Description of Study Intervention: In the intervention group, participants will receive locomotor training provided with an Ekso™ powered exoskeleton. The EAW training will be incorporated into the designated therapy times (3 hours of physical therapy (PT) and/or occupational therapy (OT)).

Study Duration: 3 years

Participant Duration: Twenty to thirty minute per session, one session a day, equal or more than 3 sessions/days per week, from enrollment in the study to discharge from the acute inpatient rehabilitation. Different participants have different duration of participation based on their length of inpatient stay.

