3 OBJECTIVES AND ENDPOINTS

OBJECTIVES	ENDPOINTS
Primary	
To determine the effects of AIR with EAW compared with AIR without EAW (same total therapy time) on the changes from admission to discharge in the International Standards for Neurological Classification of Spinal Cord Injury (ISNCSCI) upper and lower extremity motor scores, Functional Independence Measure (FIM) scores, and Spinal Cord Independence Measure (SCIM) scores as classified by clinicians.	ISNCSCI examination results FIM scores SCIM scores
Secondary	
To determine the effects of AIR with EAW compared to AIR without EAW on reducing pain using the International Spinal Cord Injury Basic Pain Data Set 2.0 (ISCIBPDS 2.0) measures where type of pain is classified with the Spinal Cord Injury Pain Instrument (SCIPI).	Intensity of pain
Tertiary/Exploratory	
To determine the effects of AIR with EAW compared with AIR without EAW on reducing a specific systemic inflammatory mediator (C reactive protein, CRP).	CRP results

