6.2 MEASURES TO MINIMIZE BIAS: RANDOMIZATION AND BLINDING

Eligible participants will be randomized into either the intervention group or the control group. In order to provide more opportunities for participants to accept EAW training, the intervention group will have 20 participants, and the control group will have 10 participants.

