9 STATISTICAL CONSIDERATIONS

9.1 SAMPLE SIZE DETERMINATION

All statistical tests will be 2-sided. The outcome measures will be tested at a 0.05 level of significance. SPSS will be used to conduct the statistical analyses. All participants who have EAW sessions will be included (regardless of the number of sessions they complete before discharge, but the number and reason of missing EAW sessions will be recorded). To test the three main hypotheses of the proposed study, the change score of each outcome between baseline and discharge will be calculated. The change score will be compared between the intervention and control groups using independent t-test analyses (if the outcomes are not normally distributed, Mann-Whitney tests will be used).

Since the primary aim of the study is to compare the improvement of FIM scores between the groups, the FIM score results from the preliminary data were used to perform the power analysis for this study. In the preliminary data, the mean change in FIM score from the intervention group was 35 ± 12 , and the control group was 22 ± 13 . The effect size of the FIM score change in our preliminary data was 1.07 (controlling for the different number of participants between the two groups). The power analysis showed that using the effect size (1.07) and 0.05 level of significance with two-sided analysis in independent t-test, a total of 30 participants will provide the study 80% power.

To account for an expected attrition rate of about 25%, 40 participants will be enrolled. It is expected that 30 participants will complete the study (the reasons and number of screening failures and dropouts will be recorded).

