9.2 STATISTICAL ANALYSES

9.2.1 GENERAL APPROACH

All statistical tests will be 2-sided. The outcome measures will be tested at a 0.05 level of significance. SPSS will be used to conduct the statistical analyses. All participants who have EAW sessions will be included (regardless of the number of sessions they complete before discharge, but the number and reason of missing EAW sessions will be recorded). To test the three main hypotheses of the proposed study, the change score of each outcome between baseline and discharge will be calculated. The change score will be compared between the intervention and control groups using independent t-test analyses (if the outcomes are not normally distributed, Mann-Whitney tests will be used).

In addition to the primary analysis, several secondary analyses will be performed. 1) Each of the outcomes will be compared between pre- and post-EAW training using a paired t-test analysis (if the outcomes are not normally distributed, Wilcoxon signed-rank test will be used). 2) Analyses will be performed to determine the relationships between the change of outcome measures and EAW training time (including sessions, up time, walking time, or total number of steps per session and across all sessions) using correlation coefficients, regression analyses (stepwise and logistic), analyses of covariance, and nonparametric analyses as appropriate. 3) An additional exploratory post

hoc analyses will be to determine the relationship of participant's baseline characteristics with successful use of the exoskeleton. This post hoc analysis would serve as pilot data to begin to determine who is a good candidate for EAW training during AIR for a future study.

References:

1. Simpson, L.A., et al., *The health and life priorities of individuals with spinal cord injury: a systematic review*. J Neurotrauma, 2012. **29**(8): p. 1548-55.
2. Ditunno, P.L., et al., *Who wants to walk? Preferences for recovery after SCI: a longitudinal and cross-sectional study*. Spinal Cord, 2008. **46**(7): p. 500-6.
3. Tate, D.G., C.Z. Kalpakjian, and M.B. Forchheimer, *Quality of life issues in individuals with spinal cord injury*. Arch Phys Med Rehabil, 2002. **83**(12 Suppl 2): p. S18-25.
4. [name], T.N. and K.T. Ragnarsson, *Pain after spinal cord injury*. Phys Med Rehabil Clin N Am, 2000. **11**(1): p. 157-68.

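### The primary endpoint is FIM alone in Section 9.1, but ISNCSCI motor scores, FIM and SCIM together in Sections 1.1 and 3, and no rule says which results make the trial positive

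*Combined protocol and SAP*

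**What the plan says.** Section 1.1 puts several scores into one primary hypothesis: "the AIR with EAW group will have significantly greater changes in ISNCSCI, FIM, and SCIM scores compared to the AIR without EAW group". Its primary endpoint covers the admission-to-discharge change in ISNCSCI "upper and lower extremity motor scores, Functional Independence Measure (FIM) scores, and Spinal Cord Independence Measure (SCIM) scores". That is three instruments, or four scores if the upper and lower extremity motor scores are tested separately. The primary row of the Section 3 table agrees: "ISNCSCI examination results FIM scores SCIM scores".

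Section 9.1 gives a different definition. The sample size paragraph opens with "Since the primary aim of the study is to compare the improvement of FIM scores between the groups", takes its effect size (1.07) from preliminary FIM data alone, and concludes that "a total of 30 participants will provide the study 80% power".

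On testing, Section 9.2.1 (repeating Section 9.1) says "The outcome measures will be tested at a 0.05 level of significance", two-sided, by independent t-test on change scores, or Mann-Whitney if the data are not normal. It adds: "To test the three main hypotheses of the proposed study, the change score of each outcome between baseline and discharge will be calculated". The three hypotheses are the primary, secondary (pain) and tertiary (CRP) ones in the synopsis. Neither section gives a testing order, an alpha split, an adjustment, or a statement of which scores must be significant.

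On allocation, Section 6.2 says "the intervention group will have 20 participants, and the control group will have 10 participants".

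**The concern.** The current text holds two definitions of the primary endpoint and no rule to choose between them. Three decision rules can be drawn from it or are left open by it:

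- **FIM alone decides.** This follows Section 9.1.
- **All primary scores must be significant.** This is the natural reading of the joined list in the synopsis hypothesis.
- **Any one significant score is enough.** Nothing says this, but nothing rules it out, since each outcome gets its own test at 0.05.

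The rules can disagree on the same data. A significant FIM result with a non-significant ISNCSCI result is a success under the first and a failure under the second. A significant SCIM result alone is a success only under the third. Section 2.1 says the trial is to determine whether the intervention is efficacious as well as feasible and safe, so what counts as success has to be fixed before the data are analysed. Otherwise the choice can follow the results.

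**Working it through.** **Inputs from the plan.** FIM effect size d = 1.07, two-sided alpha 0.05, independent t-test, 30 completers and 25% attrition (Section 9.1); 20 intervention and 10 control participants (Sections 6.1.1 and 6.2).

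**Inputs assumed.** The plan gives no effect size for ISNCSCI or SCIM and no correlations between scores. I use d = 1.07 on every score, then d = 0.8 on every score except FIM, with a common correlation from 0 to 0.9.

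**1. The plan's 80%.** Exact power comes from the noncentral t distribution with n₁ + n₂ − 2 degrees of freedom and noncentrality d·√(n₁n₂/(n₁+n₂)).

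- 15:15: 1.07 × √7.5 = 2.930, critical value 2.048, power 80.7%. The stated figure reproduces for FIM alone with equal arms.
- 20:10, as planned: 1.07 × √6.667 = 2.763, critical value 2.048, power 76.0%. A normal approximation gives 78.9%.
- 22:11: 1.07 × √7.333 = 2.898, critical value 2.040, power 80.1%. This is the smallest 2:1 design that reaches 80%: 33 completers, or 33/0.75 = 44 enrolled.

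**2. If all primary scores must be significant.** No alpha adjustment is needed, because the error of the joint claim cannot exceed that of its least favourable single test. Joint power for independent scores is the product of the single powers. With d = 1.07 throughout, that is 0.760³ = 0.44 for three scores and 0.760⁴ = 0.33 for four. With d = 0.8 on the others (single power 51.4%), it is 0.760 × 0.514² = 0.20 and 0.760 × 0.514³ = 0.10. Correlated cases were simulated as equicorrelated normal scores with pooled t-tests at 20:10 (200,000 runs).

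| Joint power at correlation | 0 | 0.5 | 0.7 | 0.9 |
|---|---|---|---|---|
| Three scores, d = 1.07 each | 44% | 55% | 60% | 67% |
| Four scores, d = 1.07 each | 33% | 49% | 56% | 65% |
| Three scores, others d = 0.8 | 20% | 32% | 37% | 44% |
| Four scores, others d = 0.8 | 10% | 24% | 31% | 40% |

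**3. If any one score is enough.** For independent scores the chance of at least one false positive is 1 − 0.95³ = 14.3% for three and 1 − 0.95⁴ = 18.5% for four. In simulation it falls to about 13% and 16% at correlation 0.5, and to about 8.5% and 9.5% at correlation 0.9.

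**4. If a Holm adjustment were added.** At Holm's first step FIM must pass 0.05/3 or 0.05/4, where its power at 20:10 is 59.0% or 54.4%. Reaching 80% at those thresholds takes 45 completers (30:15, 80.9%) or 48 (32:16, 81.0%). Full Holm does better when other scores also succeed: with d = 1.07 on every score, FIM power is about 66–69% for three and 62–66% for four. That is still short of 80% with 30 completers.

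**The case against.** The strongest reply is that the plan already shows a priority. Section 9.1 calls FIM the primary aim, every power input is FIM, and Section 2.1 frames the efficacy aim around functional independence rather than motor scores. Under that reading, or under the all-must-succeed reading, type I error is at or below 5%. The 14.3% and 18.5% belong to a rule that nothing in the text positively supports. They also assume independence, which is unlikely for FIM and SCIM, since both measure independence in function. The joint power range is wide because the plan gives no inputs for the other scores. Finally, this is a small single-site fellowship trial.

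Part of this stands. The any-one error rates are upper values for a reading that is only not excluded, and the joint power figures depend on assumptions. But if FIM is the intended primary, Sections 1.1 and 3 are wrong as written; if they are right, Section 9.1 is wrong. The text has to change on either reading. Small size does not excuse an undefined success criterion in a trial that sets out to test efficacy.

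The 76% at 20:10 arises from the allocation and would exist without the inconsistency. It matters here because naming FIM does not by itself restore the stated 80%.

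**Conclusion.** The concern holds, and the plan is wrong as written: this is a contradiction between sections, not a missing detail. It must be fixed before analysis because it can reverse the trial's conclusion.

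The stated 80% power applies, at best, to only one of the possible decision rules, and to that one only with equal arms. At the planned 20:10, FIM alone has 76.0%. Requiring all scores gives 44–67% (three) or 33–65% (four) even if every score has the FIM effect, and less if the others are weaker. The contradiction itself depends on no assumption; only the joint power and the correlated error rates do.

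The effect size is a further caution. If the plus-minus figures in Section 9.1 (35 ± 12 and 22 ± 13) are standard deviations, a difference of 13 gives d = 13/√((144+169)/2) = 1.04, or 1.05 with 20:10 weights. The preliminary group sizes are not given, so 1.07 cannot be checked. At d = 1.04–1.05, power is about 74% at 20:10 and 78–79% at 22:11.

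**What to change.** Make Sections 1.1, 3, 9.1 and 9.2.1 agree. Suggested wording: *The single primary endpoint is the change in FIM score from admission to discharge, tested at two-sided 0.05. Changes in ISNCSCI upper and lower extremity motor scores and in SCIM are secondary.* The synopsis hypothesis should be reworded to match. In Section 9.1, replace the power statement with: *With 20 and 10 completers and d = 1.07, power for FIM is 76%.*

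This follows the plan's own stated aim and power basis, and keeps alpha at 0.05 and the sample size at 30. The cost is a wording amendment, which by the compliance text before Section 1 needs IRB approval. The scientific price is that ISNCSCI or SCIM alone could no longer carry a primary claim.

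If 80% power for FIM is to be kept at 2:1, plan for 33 completers and 44 enrolled instead of 30 and 40, given d = 1.07. If the investigators do want every score to be required, they should say so and state the joint power with its assumptions. Holm should not be adopted without a new sample size.

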2 INTRODUCTION

2.1 STUDY RATIONALE

The purpose of this fellowship is to conduct a prospective, randomized controlled trial (RCT) in two groups to determine if exoskeletal-assisted walking (EAW) training, incorporated in acute inpatient rehabilitation (AIR), is a feasible, safe and efficacious approach to facilitating functional independence and reducing pain and inflammatory response in those with a spinal cord injury (SCI) who are candidates for locomotor training during AIR.

2.2 BACKGROUND

Paralysis from traumatic SCI results in an abrupt reduction in the level of daily physical activity. Depending on the neurological level and completeness of SCI, those with more severe SCI may lose neuromuscular control of the upper extremities, trunk, and/or lower extremities which can result in a loss of the ability to sit, stand and walk and to perform activities of daily living (ADLs). For people with SCI, the ability to walk consistently rank at the top of their priority list for recovery [1, 2]. Most feel that their quality of life is lower than it could be without SCI due to difficulties in independently performing daily activities, finding a job or vocation, and challenges in participating in all that a community may offer [3]. Reductions in physical activity and other physical changes also promote pain in individuals with SCI, including the two main subtypes of neuropathic and nociceptive musculoskeletal pain [4]. Approximately 80% of people with SCI experience ongoing pain [5], and about 20% of people with SCI indicate that this pain interferes with work and daily activities [6]. Furthermore, immobilization and paralysis after SCI often leads to a sedentary life style resulting in loss of muscle mass and gain of adiposity [7]. This change in ratio of muscle to fat mass predisposes to insulin resistance and the development of type II diabetes mellitus as well as to obesity [7-10]. A compromised immune system has also been reported to occur after SCI with evidence of increased markers of systemic inflammation, including elevated CRP [11-15]. Changes in cholesterol and triglyceride levels as well as immunosuppression, such as reduced natural killer, T-cell, and lymphocyte functions, have also been reported [11-16]. The inflammatory response may also play an important role in the modulation of pain after SCI [17, 18]. Clinical data shows that elevated inflammatory mediators are present in persons with acute or chronic SCI, including factors that mediate pain in preclinical models [14, 19-21]. Reductions of functional activity and increased pain and inflammatory response all worsen each other, negatively impacting an individuals' quality of life.

Locomotor training for people with SCI using body weight supported treadmill training (BWSTT) has been reported to increase muscle mass [22, 23], improve cardiovascular function [24], decrease spasticity [25], decrease pain [26], and preserve bone density [23, 27]. Although walking is considered a light intensity physical activity, a number of studies have shown clinically meaningful health benefits

from a consistent regimen of walking, in diverse populations including those who are overweight or obese [28, 29], postmenopausal [30], and elderly [31, 32]. In people with chronic obstructive pulmonary disease and peripheral artery disease, walking impairment has been associated with higher levels of systemic inflammatory cytokines [33, 34]. In persons with SCI, consistent exercise has been associated with a reduction in inflammatory mediators, e.g. CRP, as is seen in able-bodied people [35]. These data support the view that even light physical activity in persons with SCI could have clinically meaningful therapeutic effects resulting potentially in a reduction of systemic inflammation.

In theory, adding locomotor training to AIR may have the potential to improve motor recovery and functional independence through neuroplasticity. A study has shown that in an animal model locomotor training in the acute stage could improve the connectivity of the spinal neurons after SCI, resulting in reflex excitability and reduced spasticity [36]. People with SCI who participated in intensive locomotor training (five days per week for 8 weeks) using BWSTT within 6 months after SCI had a greater rate of improvement in lower-extremity motor scores than those who received this intervention in the chronic stage of SCI [37]. Patients also report the desire to begin physical training as soon as possible after acute SCI and to continue the inpatient training longer than conventionally available [38].

Powered exoskeletons are a technology that can offer overground locomotion for people with SCI who would ordinarily be unable to walk and have been suggested as a way to promote increased function and quality of life [39]. In studies pioneered by [name] (co-mentor), exoskeletons have been studied in the chronic (>6 months post) SCI population for about seven years with preliminary reports showing benefits in mobility, health and quality of life (QOL) outcomes [40, 41]. While walking in an exoskeleton, people with SCI stand upright with full weight bearing through the feet [41] and walk while activating trunk and lower limb muscles. This activation may facilitate improvements in neuroconnectivity [39]. EAW has several benefits over BWSTT. It provides ground gait training experience that offers the potential benefits of standing and gait training with just one trainer and requires less of a constant equipment space allotment in an inpatient rehabilitation setting. EAW also possesses the unique potential for use after inpatient discharge to continue training and allow functional use in home, work, and community settings.

Previous studies show that EAW can elicit moderate-intensity activity for people with SCI, and participants can learn to walk without hands-on physical assistance by another person [40, 42-44]. Subjective reports from inpatients who were given the opportunity to use an exoskeleton during AIR in Mount Sinai Hospital had comments such as: "it was really great to have the legs moving again", "walking helped with regaining trunk support" and resulted in "good sensations in the legs and feet".

Despite the potential functional and health benefits of using EAW training in persons in SCI AIR, there are few studies published that have used, or are using an EAW intervention in early inpatient rehabilitation for patients with acute/sub-acute SCI. As such, there is a critical gap in knowledge that limits the use of EAW across the clinical care spectrum in SCI: we don't know if the EAW can be

effectively incorporated in clinical practice and if adding EAW into AIR program is better than traditional AIR without EAW. We expect this prospective randomized control trial (RCT) to determine if EAW training during AIR is a feasible, safe and efficacious approach to facilitate functional independence and to reduce post-SCI pain, as well as inflammation.

